##### **3.1.2 Per-protocol (PP) Population**

The Per-Protocol (PP) population will be a subset of the Safety/FAS population and only include participants for whom evaluable data to and including Day 7 is available and with no major protocol violations.

## EXTBIO EXT608-101 Statistical Analysis Plan, V2, 2023-JULY-04

## 3.2 Data Handling Conventions

### 3.2.1 Missing Data

- Any blank value will be treated as missing (unknown)
- Blank value will be left as blank in the data listings.
- Missing data will not be estimated unless specified

### 3.2.2 Per Protocol Time Points Vs Actual Time Points

Unless specified in the analyses section, actual blood sampling times, if available, will be used for individual figures while protocol times will be used for grouping summary.

### 3.2.3 Repeated and Unscheduled Visit

A repeated visit is a visit planned, by the site, to replace a scheduled visit. Usually same data measurements as the scheduled visit will be collected.

Unscheduled visit is an unplanned visit which includes unexpected data collection.

- Whether a visit is repeated or unscheduled is determined by site and reported in the EDC.

#### 3.2.3.1 *Repeated Visit*

The principle of last observation priority will be used to handle the situation of repeated visit.

Some general recommendations are listed below:

- If a variable (except dates and all lab transferred data) is measured/collected at the repeated visit, the value from the repeated visit will be used for analyses.
- Dates and Lab transferred data will be determined case by case based on its scientifically meaningful and the date/time relative to the treatment date/time.
- If a variable is not measured / collected at the repeated visit, then the value from the original visit will be used for analyses.

#### 3.2.3.2 *Unscheduled Visit*

Unscheduled visit usually includes data not scheduled to be collected or not required by protocol.

- Data from unscheduled visit will be listed but not used for analyses, except:
  - The data be used to substitute a missing data in the scheduled visit if it clinically meaningful and within a suitable visit window. This is usually determined by the Medical Monitor.

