### 3.1.6 Individual Participant Schedule

A screening visit will take place within 28 days of dosing. Eligible participants for each cohort will be admitted to the Clinical Research Unit (CRU) 1 day prior to dosing and remain in the CRU through at least 72 hours after dosing for safety and PK assessments before discharge. The total confinement period will be 4 nights, unless extended for management of AEs at the discretion of the Investigator. The schedule of events while

inpatient is provided in [Section 7.1.1](#). Follow-up visits to the CRU will occur on/about days 5, 7, 14, 21 and 28. Participants will be monitored closely during the duration of the study for safety, PK, and PD assessments as described in [Section 3.2](#). The total duration of follow-up period may be modified in the final study design based on safety and PK data from non-clinical studies, anticipated PK/PD response and extended in individual participants as needed to observe their calcium levels return to concentrations deemed not needing further follow up.

Additional/Alternative PK/PD time points may be implemented if the Sponsor determines this is necessary to fully characterize the PK profile of EXT608.

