#### **6.1.2.2 Laboratory Data**

Data from the local laboratory will be uploaded to the Sponsor/CRO directly. A test report will be sent to the site for inclusion in the participant chart; this will be considered source data.

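### By-visit laboratory, vital-sign and ECG tables can miss abnormal values seen only at unscheduled visits, or replaced at repeated visits, and the visible SAP has no worst-post-dose summary to recover them

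*SAP*

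**What the plan says.** Three SAP rules decide which post-dose values reach the safety tables.

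- **Unscheduled visits (SAP 3.2.3.2).** "Data from unscheduled visit will be listed but not used for analyses, except" in one situation: "The data be used to substitute a missing data in the scheduled visit if it clinically meaningful and within a suitable visit window". The Medical Monitor usually makes that call.
- **Repeated visits, non-laboratory variables (SAP 3.2.3.1).** The last observation has priority. A variable ("except dates and all lab transferred data) is measured/collected at the repeated visit, the value from the repeated visit will be used") takes the later value.
- **Repeated visits, laboratory data (SAP 3.2.3.1).** "Dates and Lab transferred data will be determined case by case based on its scientifically meaningful" and on timing relative to treatment. No criterion is fixed.

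SAP 3.2.3 defines the terms: "A repeated visit is a visit planned, by the site, to replace a scheduled visit". The site decides whether a visit is repeated or unscheduled.

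The planned summaries are by time point. SAP 3.4.5.3 and 3.4.5.4 give descriptives for vital signs and ECG at each time point. SAP 3.4.5.2 summarises laboratory change from baseline and shifts in normal/abnormal status. Through SAP 3.3.4.4 and 3.3.3.5.2, those shifts compare consecutive time points, starting from baseline.

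**The concern.** The second primary safety measure (Protocol 2.1, SAP 1.2.1) concerns how often, and how severely, laboratory values, ECG and vital signs change from baseline between Day 0 and Day 28. A table restricted to scheduled visits answers a narrower question: what was seen on the planned days. After Day 7 those days are a week apart (Days 14, 21 and 28), so a transient abnormality in between can be recorded only off schedule.

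A baseline-to-worst summary is the usual way to bring such values back, and the visible SAP describes none. Nor does it define a peak serum calcium variable, although average peak serum calcium is one of the escalation criteria in Protocol 3.1.5.

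The repeat-laboratory rule adds a second weakness. SAP 3.2.4 requires decisions on major protocol violations to be documented and, in a blinded trial, made before unblinding. SAP 3.2.3.1 sets no such condition for choosing between a first and a repeat laboratory result.

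**Working it through.** The plan states no figure on this point, so there is none to reproduce. The check applies the SAP rules to short example records and then works out the weight of one participant.

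**Inputs:** the unscheduled rule (SAP 3.2.3.2), the repeat rules (SAP 3.2.3.1), the planned summaries (SAP 3.4.5.2 to 3.4.5.4 and 3.3.3.5.2), and a cohort of 3 active and 1 placebo (SAP 2.1.1). The days and values below are invented to exercise the rules.

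| Record | Value used in the table | Is the abnormal value tabulated? |
|---|---|---|
| 1. Scheduled Day 0 normal, Day 5 high, Day 7 normal; unscheduled Day 6 normal | Scheduled values only | Yes. The Day 5 trigger stays; only the Day 6 follow-up is left out |
| 2. Scheduled Days 0, 5 and 7 normal; unscheduled Day 6 high | Scheduled values only | No. The Day 6 value appears only in the listing |
| 3. Vital sign or ECG abnormal at Day 1; site repeats that visit, now normal | Repeat value | No. The first value is replaced |
| 4. Vital sign or ECG normal at Day 1; site repeats that visit, now abnormal | Repeat value | Yes |
| 5. Laboratory value at a scheduled visit and again at a repeated visit | Not determined by the SAP | Depends on an individual decision |

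Records 2 and 3 show the loss. Record 1 shows that an abnormal scheduled value is not lost because it led to an unscheduled visit. Records 3 and 4 together show that the repeat rule is blind to the value: it can remove an abnormality or bring one in.

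Record 5 assumes that laboratory transferred data means results sent electronically by the laboratory. Protocol 6.1.2.2 supports this ("Data from the local laboratory will be uploaded to the Sponsor/CRO directly"), but the SAP does not define the term. On that reading, serum calcium and the safety chemistry are exempt from automatic replacement.

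**Weight of one participant.** Suppose one of 3 active participants at a dose is affected and the value is not tabulated.

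- Counted: 1/3 = 33.3%. Exact (Clopper-Pearson) 95% limits: lower 1 − 0.975^(1/3) = 0.8%; upper, the 97.5% quantile of Beta(2, 2), = 90.6%.
- Not counted: 0/3 = 0%, with upper limit 1 − 0.025^(1/3) = 70.8%.
- Difference: 33.3 percentage points.
- Pooled placebo, if all six cohorts enrol: 6 × 1 = 6 participants, so 1/6 = 16.7% becomes 0/6.

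The intervals overlap widely, so nothing inferential turns on this. The change is in what the descriptive table shows at that dose.

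**The case against.** Much can be said for the plan.

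- **AE summaries do not depend on visit type.** SAP 3.3.4.1 captures all AEs. Clinically relevant ECG changes are also recorded as AEs (Protocol 6.7), and laboratory reports are reviewed for possible AE reporting (Protocol 6.9.3). This stands, and it limits the point to the by-visit tables. It does not close the gap, because those routes depend on clinical judgement and do not count quantitative changes.
- **Listings and individual plots carry the detail.** SAP 3.4.5.2 lists all safety laboratory results and plots each participant over time. With three active participants per dose this matters, but a listing gives no frequency, and the SAP does not say whether the plots include unscheduled values.
- **Planned tables may already cover it.** The table list is in an attached file (SAP 4), and the cohort review summaries are in a safety monitoring plan (SAP 3.5). Neither is available here, so the absence of a worst-value table is established only for the visible SAP text.
- **The rates in the illustration are not planned statistics.** Correct: the SAP plans no any-abnormality rate, so the figures show only how much one participant weighs.

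A reader might go further and infer that the plan strips out extreme values selectively. The documents do not support this. Neither rule looks at the value, and normal unscheduled results are left out too. A reader might also take "the value from the repeated visit will be used for analyses" to cover a confirmatory re-measurement within one visit. SAP 3.2.3 defines a repeat at visit level, and within-visit re-measurement is not addressed. Finally, the Protocol 3.1.6 extension of follow-up ("extended in individual participants as needed to observe their calcium levels return to concentrations deemed not needing further follow up") may look like evidence of lost peaks. It concerns recovery, and any samples after Day 28 fall outside the measure's time frame.

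**Conclusion.** The point holds for the by-visit laboratory, vital-sign and ECG tables. An abnormal value seen only at an unscheduled visit is left out unless it fills a missing scheduled value. A non-laboratory value is replaced when its visit is repeated, and repeat laboratory values are chosen without a fixed rule or a condition that the choice precede unblinding. Those tables can therefore understate the second primary safety measure.

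It would be wrong to conclude that the values prompting extra follow-up vanish, that serum calcium is automatically overwritten, or that the primary safety results as a whole are affected. Scheduled triggers stay in, laboratory data are exempt from automatic replacement, and AE summaries are untouched.

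One affected participant is a third of a cohort's active arm. How often this would occur cannot be estimated from the documents. The conclusion rests on two assumptions: that laboratory transferred data includes the local laboratory results, and that the table list not seen here holds no worst-value summary. It is a cheap improvement worth making, not a fault that undermines the design.

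**What to change.** 1. Keep the scheduled-visit rule for by-visit means.
2. For laboratories, vital signs and ECG, add the worst post-dose value and a baseline-to-worst shift, in both directions, within Day 0 to Day 28. Use all collected values: scheduled, first and repeated, and unscheduled. SAP 3.3.4.3 now limits ECG change from baseline to Days 1 to 3, so the ECG derivation would need the wider window.
3. Derive each participant's peak serum calcium from the same set of values.
4. State how a first or a repeat laboratory value is chosen for the by-visit tables, and require that choice to be fixed and documented before unblinding, as SAP 3.2.4 already does for protocol violations.

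The cost is SAP wording and one extra table per domain, with no new data collection. The downside is that participants sampled more often have more chances to show an extreme. The tables should therefore note the number of unscheduled samples.

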### 3.2.4 Major Protocol Violations and Minor Protocol Deviations

Towards the end of trial, the scientifically responsible contact (medical monitor) and the statistician will review all protocol deviations and decide if any fit the criteria of a Major Protocol Violation, for the purpose of determining if the participants satisfy the requirement of per protocol population.

## EXTBIO EXT608-101 Statistical Analysis Plan, V2, 2023-JULY-04

- The decision should be documented
- For a blinded trial, the decision should be made before unblinding

**3.2.5 Visit Window**

The following visit window is defined based on protocol.

**Table 1 Protocol Defined Visit Schedule**

Procedure	Period:	Screening	Check-in a	Inpatient Observation	Outpatient Follow-up					Early Termination
	Day -28 to Day -2	Day -1	Days 0-3	Day 5	Day 7	Day 14	Day 21	Day 28	Day 28	
		0	See In-patient sch.	0	1	1	2	2		
	Tolerance (days)									

**Table 2 Protocol Defined Sequestered Schedule for Day 0-3**

Procedure	Period	Pre-Dose		Dose	Post-Dose										
	Day	Day 0				Day 1					Day 2			Day 3	
	Time Unit	Minutes			Hour										
	Time	-120	-90	-30	0	0.25	0.5	1	1.5	2	4	8	12	18	24
	+/- Tolerance (minutes)	15	10	5	0	1	2	5	5	5	10	15	30	30	60
															60

Based on the above tables (Table 1 and Table 2), for convenience, the following visit name will be used for all analyses.

**Table 3 Visit name used in the analyses**

Screening	Day -1	Day 0-3	Day 5	Day 7	Day 14	Day 22	Day 28	Early Termination
-----------	--------	---------	-------	-------	--------	--------	--------	-------------------

## EXTBIO EXT608-101 Statistical Analysis Plan, V2, 2023-JULY-04

### 3.3 ANALYSIS VARIABLES

This section describes any reformatting, calculation or transformation that might be applied to any variable before analyses.

- Unless specified, Unit will be kept as originally reported regardless if it is Metric or American system
- If a variable is reformatted, the new format will be displayed in the data listing.
- If a variable is calculated, both the original value and the calculated value will be displayed in the data listing.
  - This usually refers to the substitution of any missing value
- If a variable is transformed for analyses, only the original value will be will be displayed in the data listing, as the transformation is usually an intermediate step in analyses.

#### 3.3.1 Demographic Characteristics Variables

Common Demographic variables include:

- Demographics
- Height weight
- Medical history
- Physical Exam

Reformatting maybe applied for display purpose but no additional calculation (except BMI) or transformation will be done before analyses.

- For Physical Exam and Medical history, if the Body system is “Other”, it will not be coded unless the “Other” category becomes the largest or 2nd to the largest category.
- Weight: Change from baseline will be calculated
  - Baseline is the weight at the beginning of visit Day -1.
- Physical Exam: Change from baseline will be evaluated
  - Baseline is Physical Exam status at screening
  - Change from baseline will be the status changes from screening to Day 28 or end of study. The following categorization will be used:
    - Normal -> Normal
    - Normal -> Abnormal
    - Abnormal -> Abnormal
    - Abnormal -> Normal
    - Unknown (if the status is missing as either of the time point)

## EXTBIO EXT608-101 Statistical Analysis Plan, V2, 2023-JULY-04

**3.3.1.1 Age**

Since only the month and year of birth are collected in the EDC, we will use number 15 to substitute the day of birth.

Then the Age will be calculated by:

$$\text{Age} = \text{Floor}\left(\frac{\text{Day 0} - (\text{The approximated Date of Birth})}{365.25}\right)$$

- Function floor means age will take the largest integer (e.g., age 50.8 will become age 50).
- For participant who is not advanced to Day 0, i.e. screening failure or randomized but not dosed, there will be no Age calculated.

**3.3.1.2 Medical History**

Reformatting maybe applied for display purpose but no additional calculation or transformation will be done before analyses.

**3.3.2 Trial conduct variables**

These include the visit dates and the study completion data of each participant. These variables are usually used for disposition or drug exposure summaries.

Reformatting maybe applied for display purpose but no additional calculation or transformation will be done before analyses unless specified in the analyses.

**3.3.2.1 Day 0**

Day 0 is anchor day used to define timeline. Based on the visit windows (section 3.2.5):

$$\text{Day 0} = \text{date of Dose (or IP administration in EDC)}$$

**3.3.2.2 Last date in study**

Last date in study is determined by site and directly reported in EDC. However, in rare case when a participant lost to follow-up and site report unknown for “last date in study”, the last known day that the participant is in clinic will be used.

**3.3.3 Efficacy Variables****3.3.3.1 Handling of (Possible) Multiple Peaks of PK Curve**

We expect the PK curve to have a single peak. However, it is possible that multiple peaks or no peak will be observed. The following are ways to handle PK curves:

1. Determination of single peak/no peak/Multi-peak will be based on the plot of the PK curve

## EXTBIO EXT608-101 Statistical Analysis Plan, V2, 2023-JULY-04

- a. The statistician will make the judgement based the visual observation of each plot of the PK curve
- 2. No peak. (i.e. the variables keep rising until the last PK measurement)
  - a. The Maximum (CMax), Time to Maximum (TMax), Time to Half-Maximum (T-Half) will be set as missing. We will consider these variables as undefined.
  - b. The AUC0-t will be calculated but the AUC0-∞ will be set as missing.
- 3. Multi-peak.
  - a. If the same Maximum value appears at two or more time point, the CMax, Time to T-Half (early) will be estimated based on the first occurrence and Time to T-Half (late)

### ***3.3.3.2 PK values at baseline, infinity, and under Lower Limitation of Qualification (LLOQ)***

PK is assumed to be 0 at baseline (i.e. prior to time 0) and at infinity.

Additionally, any PK value that is LLOQ between time 0 and infinity will be assumed to be:

- 1/2 of the value of LLOQ specification (specified in the comment for PK results by Lab), or
- 100pg/mL, if no LLOQ specification is given (default is 200 pg/mL)

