### ***3.3.3.3 Handling of missing PK time***

If PK collection time is missing but PK result is available (include LLOQ), the collection time stamp will be estimated using the scheduled time and the time 0.

For example, if the value of PK at 24 hour post dose is not missing, but the collection Time of 24 hour post dose PK is unknown. Then the collection time 24 hour post dose PK will be estimated as: T0 + 24 hour.

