#### 3.3.3.4.4 Terminal rate constant $\lambda z$

Terminal rate constant  $\lambda z$  is needed before we estimate  $AUC_{0-t}$ . Since we are expecting the terminal PK will have an exponential decline,  $\lambda z$  is estimated by:

- Find the PK after TMax
  - If there only 1 or 0 available PK readings after PK Tmax, then  $\lambda z$  will be set as missing.
- Do a regression of log-transformed PK vs Time
- $\lambda z$  is  $-1 * (\text{slope from this regression})$
- In a “No Peak” case,  $\lambda z$  will be set as missing

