#### 3.3.3.4.5 $AUC_{0-t}$

The  $AUC_{0-t}$  of PK over time will be calculated using trapezoid rule and the actual time points. Missing data for the calculation of the AUC will be handled as followed:

1. If the reading for Time 0 is missing, it will be the assumed as 0.
2. If any reading between Time 0 and Tmax is missing:
  - a. It will be imputed with linear interpolation.
3. If any reading after CMax is missing:
  - a. If  $\lambda z$  is available, it will be imputed using the regression line obtained when estimate  $\lambda z$
  - b. If  $\lambda z$  is missing,  $AUC_{0-t}$  will be set as missing.

We will calculate the following  $AUC_{0-t}$

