#### 3.3.3.4.6 $AUC_{0-\infty}$

$AUC_{0-\infty}$  is estimated as:

$AUC_{0-\infty} = AUC_{0-\text{last}} + AUC_{\text{last}}$ , where  $AUC_{\text{last}} = PK_{\text{last}}/\lambda z$ , and  $PK_{\text{last}}$  is the last available PK reading

- If  $\lambda z$  is missing, then  $AUC_{0-\infty}$  is set as missing.

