## EXTBIO EXT608-101 Statistical Analysis Plan, V2, 2023-JULY-04

## 7 Revision History

Version	Summary
1.0	Initial Document
2.0	

1.Add sections dealing with different LLOQ used by the PK Lab

2.Clarified how to handle missing values in PK

3.Corrected few typos

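### The SAP replaces every post-dose below-LLOQ sample with half the LLOQ and lets that constant into lambda-z and the AUCs; with about three or more trailing below-LLOQ samples, half-life can be inflated several-fold, and AUC mainly at low doses

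*SAP*

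**What the plan says.** SAP 3.3.3.2 covers all post-dose below-LLOQ results, wherever they fall in the profile: "Additionally, any PK value that is LLOQ between time 0 and infinity will be assumed to be" half of the laboratory's LLOQ, or "100pg/mL, if no LLOQ specification is given (default is 200 pg/mL".

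The later steps take these values as data:

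- SAP 3.3.3.3, on missing collection times, counts a below-LLOQ result as a result: "PK result is available (include LLOQ".
- SAP 3.3.3.4.4 takes the readings after Tmax and says "Do a regression of log-transformed PK vs Time". Apart from a no-peak profile, lambda-z is missing only under the condition "If there only 1 or 0 available PK readings after PK Tmax". Two readings are therefore enough, and they may both be substituted constants.
- SAP 3.3.3.4.5 applies the trapezoid rule to the series. Missing post-Cmax readings are filled from the fitted line ("it will be imputed using the regression line obtained when estimate"), but a substituted value is not missing. Table 4 runs to 28 days.
- SAP 3.3.3.4.6 adds a tail of PK_last/lambda-z, where PK_last "is the last available PK reading", not the last quantifiable one.
- SAP 3.3.3.4.7 to 3.3.3.4.9 derive the late half-life, CL/F and Vz/F from these quantities.

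Protocol 2.2 lists the affected parameters as secondary objectives. Protocol 8.3 assesses dose proportionality with a power model.

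**The concern.** Once a participant drops below the LLOQ, each later sample becomes the same number. On the log scale that is a flat tail, and a regression through all post-Tmax points is pulled towards it. Lambda-z is then too small and half-life too long. The tail PK_last/lambda-z suffers twice: its numerator is a substituted constant and its denominator is too small.

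EXT608 is being developed for an extended half-life (Protocol 1.2), and Protocol 3.3.1 intends to model multiple-dose PK from these single-dose data. When this error is large, it makes half-life longer. The AUC part shrinks as dose rises, so it also tilts the power-model slope below 1 when exposure is truly proportional.

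**Working it through.** **Inputs from the documents.** Default LLOQ 200 pg/mL (SAP 3.3.3.2). Starting dose 4 µg, up to six cohorts, steps of at most 3-fold (Protocol 3.1.2), so the steepest ladder is 4, 12, 36, 108, 324, 972 µg. Follow-up visits on Days 5, 7, 14, 21 and 28 (Protocol 3.1.6).

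**Assumed, because the documents give no values.** One compartment, first-order absorption, no noise, and the V/F, half-life, LLOQ and PK days stated below.

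**1. The SAP's own figure.** 200/2 = 100 pg/mL. It reproduces.

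**2. One profile by hand.** Take 4 µg, V/F 10 L, true half-life 48 h, absorption rate 0.5/h, LLOQ 200, samples over 0.25–72 h and then Days 5 to 28.

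- Dose/V = 400 pg/mL and true lambda = ln 2/48 = 0.01444/h, so true AUC0-inf = 400/0.01444 = 27,700 pg·h/mL. Since 672 h is 14 half-lives, true AUC0-28d is practically the same.
- Peak is 359 pg/mL. Six post-Tmax samples fall below 200 and are set to 100.
- The SAP regression gives half-life 436.2 h: 436.2/48 = 9.1x.
- The SAP AUC0-28d is 77,064: 77,064/27,700 = 2.8x.
- Tail = 100 × 436.2/0.6931 ≈ 62,930. AUC0-inf ≈ 77,064 + 62,930 ≈ 139,990: 5.05x. CL/F is 1/5.05 = 0.20x and Vz/F is 9.1/5.05 = 1.8x.
- With below-LLOQ values left out of lambda-z and the tail taken from the last quantifiable sample: half-life 48.0 h, AUC0-inf 27,542.

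Under the same assumptions the SAP gives half-life 3.9x and AUC0-inf 1.85x at 12 µg, and 1.26x and 1.06x at 972 µg. The power-model exponent for AUC0-inf over the six doses is 0.75, against a truth of 1.00.

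**3. A less favourable case.** True half-life 24 h, V/F 10 L, LLOQ 200, absorption half-life 2 h, SAP Table 2 hours plus Days 2, 3, 5, 7, 14, 21, 28. Half-life and AUC0-inf are 27x and 12x at 4 µg, 6.2x and 1.6x at 36 µg, 2.6x and 1.06x at 972 µg.

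**4. A grid.** 60 combinations per dose (LLOQ 50–200 pg/mL, half-life 24–336 h, V/F 5–50 L), otherwise as in step 3. These are not probabilities. Ratio of the SAP result to truth, sampling to Day 28:

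| Trailing below-LLOQ samples | Half-life | AUC0-inf |
|---|---|---|
| 1 | 0.76–1.11x | 0.84–1.05x |
| 2 | 0.79–1.55x | 0.86–1.13x |
| 3 | 1.02–3.44x | 1.00–1.63x |
| 4 | 2.7–5.0x | 1.1–2.1x |
| 5 or more | 1.8–52x | 1.4–26x |

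AUC0-inf exceeds 2x in 34 profiles, all with Cmax 1.0–8.6 times the LLOQ.

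Scenarios with half-life off (above 1.25x or below 0.8x), out of those where the SAP gives a finite value, by last PK sample:

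| Dose | Day 3 | Day 7 | Day 14 | Day 28 |
|---|---|---|---|---|
| 4 µg (of 45) | 7 | 15 | 22 | 30 |
| 12 µg (of 59) | 4 | 14 | 25 | 37 |
| 36 µg (of 60) | 1 | 4 | 19 | 29 |
| 108 µg (of 60) | 0 | 1 | 15 | 25 |
| 972 µg (of 60) | 0 | 0 | 6 | 18 |

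**5. No quantifiable value after Tmax.** All post-Tmax values are equal, so the slope and lambda-z are 0. SAP 3.3.3.4.4 does not set this to missing, and ln 2/lambda-z, PK_last/lambda-z, CL/F and Vz/F are undefined. A wholly below-LLOQ profile still receives AUC0-28d of about 100 × 672 = 67,200 pg·h/mL. This accounts for the 60 − 45 = 15 scenarios absent at 4 µg and the 60 − 59 = 1 at 12 µg.

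**6. The remedy in the same grid.** With at least three quantifiable post-Tmax points, a negative slope and the tail from the last quantifiable sample, half-life is 1.00–1.12x and AUC0-inf 0.99–1.07x of truth where estimable.

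**The case against.** The strongest reply is that the size rests on PK that nobody can see. That stands. EXT608 is meant to have a long half-life, and with a true half-life of 96 h or more only 5 of 36 scenarios at 36 µg are off, and none of 36 at 324 or 972 µg. The last PK day is decisive: Protocol 6.9.4 points to the inpatient schedule, and if sampling ended at Day 3 little remains. AUC0-28d as a named endpoint, and PK monitoring through follow-up (Protocol 3.1.6), make later draws likely but do not prove them. The largest multiples belong to a dose whose peak is under twice the LLOQ, where any rule struggles.

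Four stronger readings are tempting, and the documents do not support them.

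- A reader might infer that escalation is compromised. DMB packages do include PK, but the written rules in Protocol 3.1.5 use AEs and serum calcium.
- A reader might infer from "Add sections dealing with different LLOQ used by the PK Lab" in the SAP revision history that identical curves in this trial received different half-lives. The line does not say how different limits were applied within the dataset.
- A reader might say that the SAP has no rule at all for a flat profile. SAP 3.3.3.1 provides for no-peak profiles by visual judgement and for tied maxima. The no-peak text describes a rising curve, and the tie rule leaves lambda-z at 0. If the statistician did call a flat profile no-peak, lambda-z would be missing, but AUC0-t would still be calculated from the constant.
- A reader might fold in the unrestricted post-Tmax fit. With a two-phase decline and no sample below the LLOQ, that fit gives half-life 0.67–0.89x. It is a separate and opposite bias.

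**Conclusion.** The concern holds as a conditional one. From the text alone, substituted constants enter lambda-z, AUC0-28d and PK_last, and a flat post-Tmax series gives an undefined half-life. How much this matters depends on how many samples trail below the LLOQ. With one or two, with a long half-life, or with sampling that ends at Day 3, the bias is mostly small and can run downwards. With about three or more, half-life is inflated, up to several-fold. AUC0-28d and AUC0-inf are inflated mainly where Cmax is within about 10 times the LLOQ.

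Every multiple above depends on the assumed model, V/F, half-life, LLOQ and sampling days. The direction and the dependence on trailing samples appeared under two different sets of assumptions. These are descriptive secondary endpoints with no formal testing (Protocol 8.3). SAP 3.3 lists original beside substituted values, so the error can be recovered if someone notices it. It should be fixed, but it does not threaten the primary safety objective.

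**What to change.** 1. SAP 3.3.3.2: do not substitute half the LLOQ after the last quantifiable sample.
2. SAP 3.3.3.4.4: fit lambda-z only on quantifiable post-Tmax values, at least three. Set it to missing if there are fewer or if the slope is not negative. Report the fit window (first time, last time, number of points) with each half-life.
3. SAP 3.3.3.4.6: end AUC0-last, and start the tail, at the last quantifiable concentration.
4. SAP 3.3.3.4.5: state how trailing below-LLOQ samples enter AUC0-28d, for example from the terminal line, or with the AUC missing if lambda-z is missing. Amend item 3a so that it does not conflict with the handling of below-LLOQ values between quantifiable samples.
5. Wholly below-LLOQ profiles: report Cmax as below LLOQ and the other parameters as not estimable, and report how many are left out of the power model.

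The cost is SAP wording and programming, plus some lost estimates. In the grid, 16 of 60 scenarios at 4 µg and 4 of 60 at 12 µg become not estimable. Of these, 15 and 1 are already undefined under the SAP, so the net loss is 16 − 15 = 1 and 4 − 1 = 3. Real data would lose more: with 20% residual error in the 24 h case of step 3, 61.5% of 4 µg profiles have fewer than three usable points. No rule recovers a terminal phase that lies below the LLOQ, which is why the fit window should be reported. Choosing terminal points by adjusted R-squared, or capping imputed values at the LLOQ, is optional and separate.
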